1.2 STUDY DESIGN

Study 2009 is an operationally seamless 2-part, phase 2/3, prospective, global, multicenter, randomized, double-blinded, placebo (PBO) -controlled study to investigate the efficacy, safety, tolerability, immunogenicity, PRO measures (including QoL assessments), PK, and PD of EFG PH20 SC in adult participants with moderate-to-severe BP.

During both parts of the study, participants will be administered investigational medicinal product (IMP: EFG PH20 SC or PBO PH20 SC) once weekly for 36 weeks. All participants will also receive concurrent therapy with oral corticosteroids (OCS), i.e., prednisone at a starting dosage of 0.5 mg/kg/day at baseline, or an alternate OCS at an equivalent dose strength. The OCS dosage will be adjusted according to each participant's BP disease status throughout the study.

Part A is a phase 2, proof-of-concept study in which approximately 40 adult participants with moderate-to-severe BP will be randomly assigned to treatment with either EFG PH20 SC or PBO PH20 SC. The main goal of part A is to determine whether EFG PH20 SC is effective in the treatment of participants with BP via assessment of the study's primary endpoint: the proportion of participants who are in complete remission (CR) while receiving efgartigimod PH20 SC or placebo and have been off OCS therapy for ≥8 weeks at week 36. Other part A objectives and endpoints are listed in section 1.1.1.

An interim analysis (IA) will be conducted from data obtained from all part A participants through the week 26 visit. The IA will be conducted to assess the primary endpoint, assess several of the study's secondary endpoints, confirm the appropriate sample size for part B of the study, and determine whether the efficacy results observed through week 26 warrant continued study of EFG PH20 SC for the treatment of participants with BP (futility analysis).

[figure not shown]
The final analysis of part A data will be performed after its last participant completes their last visit.

Part B is a phase 3, confirmatory study in which approximately 120 adult participants with moderate-to-severe BP will be randomly assigned to treatment with either EFG PH20 SC or PBO PH20 SC. The main goal of part B is to confirm the results obtained for the primary endpoint from part A (the proportion of participants who are in CR while receiving efgartigimod PH20 SC or placebo and have been off OCS therapy for ≥8 weeks at week 36), but in a separate and larger group of participants. Other part B objectives and endpoints are listed in section 1.1.2. The proposed order of the key secondary endpoints for part B may be adjusted based on the results obtained in the IA of part A of the study.

1.3 EXPECTED SAMPLE SIZE

Part A: Approximately 40 adult participants with moderate-to-severe BP will be randomly assigned in a 1:1 ratio to one of the following study intervention groups:

- EFG PH20 SC
- PBO PH20 SC

Part B: Approximately 120 adult participants with moderate-to- severe BP will be randomly assigned in a 1:1 ratio to one of the following study intervention groups:

- EFG PH20 SC
- PBO PH20 SC

Participants who reach the End of Treatment Period (EoTP) visit (week 36) will be offered the option to either roll over into a long-term, open-label extension (OLE) study (ARGX-113-2010) or complete a 7-week treatment-free follow-up period.

1.4 INTERIM ANALYSIS

An IA will be performed during part A of the study. Results of the IA will help supporting the sponsor's decision whether to continue part B of the study as currently designed, modify the sample size for part B, or discontinue the study (both parts A and B) due to lack of efficacy.

The IA of part A will be performed using data collected from all of its participants through the data cutoff time point (defined as the last participant in part A reaching week 26).

Both part A and part B of the study are randomized and double-blinded. Section 1.4.4 provides the measures to ensure that blinding and integrity of the part A dataset is maintained while the unblinded IA is being performed.

1.4.1 Futility analysis

A futility analysis will be performed using the analysis of the primary endpoint at the IA cutoff time point.

[figure not shown]
1.4.1.1 ENDPOINT USED FOR THE FUTILITY ANALYSIS

The primary endpoint will be used for the futility analysis. The primary endpoint is a binary endpoint. A subject is considered a responder (Y) if he or she is in CR while receiving efgartigimod PH20 SC or placebo and is off OCS therapy for ≥ 8 weeks at week 36. Otherwise, the subject is considered a non-responder (N).

1.4.1.2 MISSING DATA IMPUTATION

All missing data imputation rules specified in Section 4.1.2.2 for the primary endpoint will be applied. At the IA cutoff time point, some subjects will have not completed the treatment period. As specified in Section 4.1.2.2, absence of data due to premature study termination or a subject failing to perform the disease assessment at week 36 will be handled using the composite strategy (i.e., subject considered as non-responder).

However, for the IA one more imputation rule is required to handle the fact that some subjects will still be ongoing by the time of data cutoff. For ongoing subjects only, a surrogate endpoint will be defined as 'being in CR while receiving efgartigimod PH20 SC or placebo and is off OCS therapy for ≥8 weeks at last visit'. Derivation of this endpoint follows the same rules and strategies planned in Section 4.1.2.2for the primary endpoint but replacing 'week 36' by 'week X' which will represent subject's last visit before cutoff time point.

For ongoing subjects, the above surrogate endpoint will be used as a proxy (substitute) of the primary endpoint at the IA.

Also, for key secondary endpoints with evaluation at week 36, a surrogate endpoint will be used replacing 'week 36' by 'week X' which will represent subject's last visit before cutoff time point.

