6.8.1.3. Oral Prednisone Dose Adjustment Regimen (Based on BP Disease Assessment)

Participants will receive IMP with concurrent OCS therapy. The recommended OCS dosing regimen is described below and displayed in Table 7.

The investigator should not deviate from the concurrent oral prednisone dosing regimen, except in matters where the safety of the participant may be compromised. After taking appropriate action to ensure the safety of the participants, such concerns should be documented and communicated to the sponsor's medical monitor and designee within 24 hours of the event.

For OCS doses not listed in Table 7, minimum and maximum recommended doses are provided. For participants with body weights of <45 kg or ≥110 kg, the investigator should propose OCS doses and inform the medical monitor to ensure consistency within the study.

Note: For the following list, "oral prednisone" refers to prednisone or an alternate OCS of equivalent dose strength.

- All participants will begin the study by taking oral prednisone 0.5 mg/kg/day starting at baseline (week 0; day 1).
- If the participant has not achieved CDA within 1-3 weeks of treatment with oral prednisone 0.5 mg/kg/day, then the dosage may be increased to 0.75 mg/kg/day for up to an additional 3 weeks. This period may be extended by 1 additional week (based on clinical judgment) to achieve CDA with an oral prednisone dosage of either 0.75 mg/kg/day or 1 mg/kg/day.

- A participant will be considered as a treatment failure if they do not achieve CDA after receiving the IMP with the prednisone dosing regimen described above. In case of treatment failure, IMP will be permanently discontinued (Section 7.1.1). Under these circumstances, the participant will be considered a nonresponder (Section 9.3.2).
- When CDA is achieved, the oral prednisone dosing regimen is adjusted as follows:
 - After CDA has been sustained for ≥2 weeks, the dose tapering schedule begins with the next lower oral prednisone dosage as listed in Table 7. Each new dosage must be maintained for at least 2 weeks provided that no new lesions (transient or nontransient) appear. Duration of tapering steps from escalated doses (>0.5 mg/kg/day) may be shortened based on clinical judgment.

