 - For participants who achieved CDA on oral prednisone 0.5 mg/kg/day, the tapering steps are 0.3, 0.2, 0.15, and 0.1 mg/kg/day. For participants who required a dose increase to 0.75 or 1.0 mg/kg/day to achieve CDA, the oral prednisone dosage must first be tapered down to 0.5 mg/kg/day before proceeding to 0.3, 0.2, 0.15, and 0.1 mg/kg/day as shown in Table 7.
 - Further tapering below the level of minimal OCS therapy can be performed in steps of 2.5 mg/day until the participant is off oral prednisone therapy (Table 7). Each new dosage step must be maintained for at least 2 weeks, provided that no new lesions (transient or nontransient) appear.
 - If a participant has new lesions after the start of OCS tapering (ie, after CDA has been sustained for ≥2 weeks) but the investigator determines that it is not a relapse, prednisone tapering will be delayed. Under these circumstances, tapering can resume when no new lesions have appeared for at least 1 week (Table 7).
- If a participant relapses:
 - The oral prednisone dosage is increased based on the clinical judgment of the investigator, with the recommendation to return to the dose administered 2 tapering steps before the relapse. Tapering can be resumed after CDA has been sustained for at least 2 weeks on this increased dose.
 - If CDA is not achieved, the participant should resume the initial oral prednisone dosage of 0.5 mg/kg/day.
 - The participant must resume weekly on-site visits until CDA returns.

For concurrent oral methylprednisolone equivalent doses, refer to Table 16.

For home study visits that occur between mandatory on-site visits, the investigator will call the participant once weekly to review the participant's BP disease status and current oral prednisone (or equivalent) dosing regimen (Section 8.1.4).

Table 7: Concurrent Oral Prednisone Equivalent Doses (in mg) Based on Participant Body Weight

Table /.		Body weight category ^a													
Oral prednisone dose level	<45 kg	≥45 to <50 kg	≥50 to <55 kg	≥55 to <60 kg	≥60 to <65 kg	≥65 to <70 kg	≥70 to <75 kg	≥75 to <80 kg	≥80 to <85 kg	≥85 to <90 kg	≥90 to <95 kg	≥95 to <100 kg	≥100 to <105 kg	≥105 to <110 kg	≥110 kg
level	Minimum recommended daily OCS doses		Daily OCS doses ^b									Maximum recommended daily OCS doses			
mg/kg/day								mg/day	7						
1.0	40	45	50	55	60	65	70	75	80	85	90	95	100	105	110
0.75	30	30	35	40	45	45	50	55	60	60	65	70	75	75	80
Starting dose: 0.50	20	22.5	25	25	30	30	35	35	40	40	45	45	50	50	60

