1.4.1.4 FUTILITY ANALYSIS RECOMMENDATION ALGORITHM

The target value (TV) was defined in the CSP as an absolute treatment difference (EFG vs. PBO) of 30%. Similarly, the lower reference value (LRV) was defined as an absolute treatment difference (EFG vs. PBO) of 10%.

The futility analysis recommendation algorithm is as follows:

- The recommendation will be to continue the study ("Go") if LL80 > LRV and UL90 > TV.
- The recommendation will be to stop the study ("Stop") if UL90 ≤ TV.
- The outcome will be considered inconclusive ("Consider") otherwise.

Figure 1 illustrates the probability of each of the planned recommendations for each value of the EFG responder rate while holding the PBO rate to 20%.

[figure not shown]
[figure not shown]

Figure 1. Probability of recommendation vs. EFG responder rate (PBO rate fixed at 20%)

In case the recommendation is 'consider', the analysis of the key secondary endpoints will be reviewed to make a final decision.

This document considers the above as recommendations and acknowledges the possibility of deviations from the above algorithm. If the recommendation is 'stop', it is also possible that the sponsor decides to not stop the study (e.g., if the analysis of key secondary endpoint suggests a clinically meaningful effect).

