1.4.2 Sample size re-adjustment

1.4.2.1 STATISTICAL CALCULATION

The unadjusted proportions of primary endpoint response (after implementing the proxy imputation method defined above) will be used to calculate the sample size required in part B to achieve a 90% power.

[figure not shown]
The following SAS script will be used to obtain the required sample size:

```
proc power;
twosamplefreq test = pchi
groupproportions = (0.X 0.Y)
ntotal = .
power = 0.9;
run;
```

Figure 2 illustrates the distribution of the obtained required sample sizes vs. the observed treatment difference after using 100,000 simulations of part A trial (n = 20 per arm) assuming 20% rate with PBO and 50% rate with EFG.

SGS	Statistical Analysis Plan	
ARGX-113-2009	Final and Interim Analysis	Final 4.0 of 04NOV2024

Figure 2. Observed absolute difference in part A and resulting required sample size in part B

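### The interim scores participants not yet at week 36 on remission off OCS at their last visit, which can count slower week-36 responders as failures, and the described operating characteristics do not mention this

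*SAP*

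**What the plan says.** SAP 1.4 sets the interim cut-off as "defined as the last participant in part A reaching week 26". Those randomised early enough will have passed week 36 and are scored on the real endpoint. The others are at about weeks 26 to 35. For them, SAP 1.4.1.2 replaces week 36 by the last visit before cut-off and states: "For ongoing subjects, the above surrogate endpoint will be used as a proxy (substitute) of the primary endpoint at the IA".

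The proxy feeds two rules:

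- **Futility (SAP 1.4.1.3–1.4.1.4).** The target value is a 30-point difference and the lower reference value is 10 points. Go needs LL80 above 10 and UL90 above 30. "The recommendation will be to stop the study" if UL90 is at or below 30.
- **Sample size (SAP 1.4.2.1–1.4.2.2).** "The unadjusted proportions of primary endpoint response (after implementing the proxy imputation method defined above) will be used" to find the Part B total for 90% power. A result of 120 or less leaves 120 in place; a larger one may raise it.

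Protocol 6.8.1.3 and Table 7 set the fastest route off OCS. "After CDA has been sustained for ≥2 weeks, the dose tapering schedule begins". For participants controlled on the starting dose, "the tapering steps are 0.3, 0.2, 0.15, and 0.1 mg/kg/day". "Each new dosage must be maintained for at least 2 weeks provided that no new lesions (transient or nontransient) appear". Below the minimal-OCS level, Table 7 adds zero to three further steps by weight, and "Each new dosage step must be maintained for at least 2 weeks".

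The text for SAP Figure 1 gives a placebo rate fixed at 20% with the efgartigimod rate varied. The text for Figure 2 gives 20% and 50% with 20 per arm. Neither mentions the proxy, and no correction or sensitivity analysis for it is planned.

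**The concern.** CRoff has a built-in lag: sustained control, a stepwise taper, then 8 weeks off OCS. A participant at week 28 may be following the protocol exactly, be off OCS already, and still not qualify until after cut-off. The proxy records that participant as a non-responder, although the thresholds of 30 and 10 points refer to an endpoint defined at week 36.

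The main stake is a mistaken Stop or Consider for a drug that meets its target. A secondary stake is an inflated Part B size. The Adaptation Committee would also be reading its result against operating characteristics described only in terms of simple response rates.

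**Working it through.** **1. The plan's own figure.** Protocol 9.5 says 120 participants give more than 90% power (two-sided 5%, 1:1). The rates there are redacted, so I use the 20% and 50% of SAP 1.4.2.1. At 60 per arm, power is 94.1% by the two-proportion formula and 91.3% by exact Fisher. The statement reproduces.

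Required size, chi-square test at 90% power:

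n per arm = [1.96·√(2p̄(1−p̄)) + 1.2816·√(p₁(1−p₁) + p₂(1−p₂))]² / (p₁−p₂)²

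With p₁ = 0.5, p₂ = 0.2 and p̄ = 0.35: (1.96 × 0.6745 + 1.2816 × 0.6403)² / 0.09 = 51.01. That is 52 per arm, or 104 in total.

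**2. Earliest CRoff under the taper.** CDA week + 2 + (4 × 2) + (2 × extra steps) + 8.

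| Weight (kg) | Extra steps | CDA to CRoff (weeks) | Latest CDA for CRoff at week 26 | Latest CDA for CRoff at week 36 |
|---|---|---|---|---|
| <50 | 0 | 18 | 8 | 18 |
| 50 to <75 | 1 | 20 | 6 | 16 |
| 75 to <100 | 2 | 22 | 4 | 14 |
| ≥100 | 3 | 24 | 2 | 12 |

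Putting in the CDA times the protocol allows, by weight band in the same order:

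- No escalation, no delay, CDA at weeks 1–3: CRoff at weeks 19–21, 21–23, 23–25 and 25–27.
- Escalated to 0.75 mg/kg, CDA at weeks 4–7, with 2 weeks at 0.5: weeks 24–27, 26–29, 28–31 and 30–33. Shortening the 0.5 step brings these forward by up to 2 weeks.
- Escalated to 1.0 mg/kg, CDA at week 7: weeks 29, 31, 33 and 35.

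Every path can succeed by week 36. Most escalated paths at 50 kg or more miss week 26.

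**3. Share ongoing.** Accrual is not stated. With uniform accrual over T weeks, those randomised in the last 10 weeks have not reached week 36, so the share is 10/T: 19% for T = 52 (about 8 of 40) and 38% for T = 26 (about 15 of 40). I use 20% and 40%.

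**4. Effect if both arms are affected equally.** Let f be the share ongoing and v the share of their eventual responses already visible. Observed rate = true rate × [1 − f(1−v)]. Probabilities are exact binomial at 20 per arm with Wald 60% and 80% limits.

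| f | v | Observed rates | Go | Stop | Required N |
|---|---|---|---|---|---|
| 0 | – | 50% / 20% | 70% | 11% | 104 |
| 20% | 70% | 47% / 18.8% | 66% | 13% | 114 |
| 20% | 50% | 45% / 18% | 63% | 15% | 122 |
| 20% | 30% | 43% / 17.2% | 60% | 17% | 130 |
| 40% | 70% | 44% / 17.6% | 62% | 16% | 126 |
| 40% | 50% | 40% / 16% | 56% | 20% | 144 |
| 40% | 30% | 36% / 14.4% | 50% | 26% | 166 |

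Single-stratum Klingenberg limits show the same pattern. Stop is 11.4% with no proxy, 14.1% (N 114) at T = 52 with a third of responses not yet visible, and 27.4% (N 164) at T = 26 with 70% not yet visible.

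**5. Effect if the arms differ.** Take T = 26, so f = 10/26 = 0.385, with Klingenberg limits.

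- Not yet visible: 20% of efgartigimod and 70% of placebo responses. Rates are 0.5 × (1 − 0.385 × 0.2) = 46.2% and 0.2 × (1 − 0.385 × 0.7) = 14.6%. The difference is 31.5 points and Stop falls to 9.1%.
- The reverse: 36.5% and 18.5%. The difference is 18.1 points and Stop rises to 36.5%.

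**The case against.** Four counter-arguments have force.

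- **How many are affected is not shown.** A reader might infer from the table in step 2 that CRoff is out of reach at the interim for many eventual responders. The documents do not support that. The undelayed, unescalated path reaches CRoff at weeks 19–27 and misses week 26 only at ≥100 kg with CDA at week 3. The treatment-failure rule (Protocol 4.1.3 and 6.8.1.3) also puts first CDA at about week 7 at the latest on the full sequence (3 + 3 + 1 weeks), so the later CDA times in the last column are mostly not open to first responders. The share escalated, delayed or relapsed is not given, and week 26 is the worst case among ongoing participants.
- **Direction.** A reader might also infer that both rates and their difference must shrink. Step 5 shows that the difference can widen. A proxy responder can also relapse before week 36, which works the other way; Protocol 4.2.4.1 notes that relapse within months is common.
- **Sample size.** With the floor of 120 and only an option to increase, the usual error is extra power. Part B is a separate group of participants, so its type I error for the primary endpoint is untouched by the proxy.
- **Safeguards.** The futility rule is non-binding, and Protocol 4.2.1 openly describes a week-26 look. Consider leads to review of the key secondary endpoints, and these may also justify overriding a Stop. This helps only in part, because SAP 1.4.1.2 applies the same substitution to key secondaries evaluated at week 36. NCOD and itch do not need 8 weeks off OCS.

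Replacing the proxy outright would also have a price. With 12 per arm and no effect (20% versus 20%), correct Stops fall from 85.5% to 74.2% and false Go rises from 4.9% to 7.9%, compared with 20 per arm (Wald limits). At a true 50% versus 20%, 12 per arm gives Go 55% and Stop 10%; 16 per arm gives 70% and 11%.

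**Conclusion.** The point stands in limited form. The text is explicit that ongoing participants are scored early on a lagged endpoint and that both rules use the result. Some participants who could respond at week 36 will be counted as failures, so rates are probably understated, but neither the amount nor the effect on the difference can be fixed from the documents. Under equal effect in both arms at 50% versus 20%, Stop rises from about 11% to 13–26% and required N from 104 to 114–166. This rests on assumed ongoing shares of 20–40%, assumed visible shares of 70–30%, no loss of response after the last visit, and unstratified limits in place of the SAP's strata-adjusted ones. The described operating characteristics, as far as the text shows (the figures were not available), are not those of the proxy rule. The case supports adding an analysis, not discarding the proxy.

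**What to change.** In SAP 1.4.1.2 to 1.4.2:

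1. Keep the proxy analysis. Alongside it, give the Adaptation Committee LL80, UL90, the resulting recommendation and the required N from participants randomised at least 36 weeks before cut-off, whatever their status. Selecting on randomisation date keeps the restriction unrelated to outcome.
2. Optionally, add a version with week-36 status imputed for ongoing participants from current disease status and OCS dose.
3. State that neither a Stop nor an increase in N should rest on the proxy alone when the two analyses disagree.
4. Re-simulate Figures 1 and 2 with the proxy applied, over a range of ongoing shares and including unequal timing between arms.

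The cost is SAP wording and a little programming, with no delay to the interim. The second estimate is less precise: 24 to 32 of 40 participants if 20–40% are ongoing. It may therefore produce more Consider outcomes.

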1.4.1.3 STATISTICAL ANALYSIS

The primary endpoint will be analyzed as detailed in Section 4.1.2. The primary estimand (composite strategy) will be used. In particular, the futility decision-making algorithms will be implemented instead of the estimated Klingenberg strata-adjusted difference in proportions. For this statistic, a standard two-sided 95% confidence interval will be first produced as plan for the final analysis. However, these values are not the ones to be used by futility analysis recommendation algorithm (Frewer et al.). These other confidence interval limits will also be obtained at the IA using the same SAS code (Proc FREQ) proposed for the final analysis:

- Lower limit of the two-sided 60% confidence interval. This value will be denoted as LL80 because, if this value is interpreted using Bayesian thinking, we could say that the treatment effect (in the absolute difference scale) will be greater than LL80 with a (posterior) probability > 80%.
- Upper limit of the two-sided 80% confidence interval. This value will be denoted as UL90 because, it could be interpreted that the absolute difference (EFG vs. PBO) will be smaller than UL90 with a probability > 90%.

1.4.1.4 FUTILITY ANALYSIS RECOMMENDATION ALGORITHM

The target value (TV) was defined in the CSP as an absolute treatment difference (EFG vs. PBO) of 30%. Similarly, the lower reference value (LRV) was defined as an absolute treatment difference (EFG vs. PBO) of 10%.

The futility analysis recommendation algorithm is as follows:

- The recommendation will be to continue the study ("Go") if LL80 > LRV and UL90 > TV.
- The recommendation will be to stop the study ("Stop") if UL90 ≤ TV.
- The outcome will be considered inconclusive ("Consider") otherwise.

Figure 1 illustrates the probability of each of the planned recommendations for each value of the EFG responder rate while holding the PBO rate to 20%.

[figure not shown]
[figure not shown]

Figure 1. Probability of recommendation vs. EFG responder rate (PBO rate fixed at 20%)

In case the recommendation is 'consider', the analysis of the key secondary endpoints will be reviewed to make a final decision.

This document considers the above as recommendations and acknowledges the possibility of deviations from the above algorithm. If the recommendation is 'stop', it is also possible that the sponsor decides to not stop the study (e.g., if the analysis of key secondary endpoint suggests a clinically meaningful effect).

